4.5.5. Cohort B Primary Efficacy Variable

The primary efficacy variable for Cohort B is:

- Proportion of subjects who subsequently develop signs and symptoms (broad-term) within 14 days of a positive RT-qPCR at baseline or during the EAP

4.5.6. Cohort B Key Secondary Efficacy Variables

The key secondary efficacy variables listed below are continuous (C) variables.

Key Secondary Efficacy Variables	Type
Number of weeks of symptomatic SARS-CoV-2 infection (broad-term) within 14 days of a positive RT-qPCR at baseline or during the EAP	C
Number of weeks of high viral load >4 (log10 copies/mL) in NP swab samples during the EAP	C

4.5.7. Cohort B and Cohort B1 Other Secondary Efficacy Variables

The secondary efficacy variables listed below include two types of variables: binary (B) and continuous (C) variables and marked for the corresponding cohort.

Other Secondary Efficacy Variables	Type	Cohort	
		B	B1
Proportion of subjects who subsequently develop signs and symptoms (CDC definition) within 14 days of a positive RT-qPCR at baseline or during the EAP	B	X	X
Proportion of subjects who subsequently develop signs and symptoms (strict-term) within 14 days of a positive RT-qPCR at baseline or during the EAP	B	X	X

Number of weeks of symptomatic SARS-CoV-2 infection (CDC definition) within 14 days of a positive RT-qPCR at baseline or during the EAP	C	X	X
Number of weeks of symptomatic SARS-CoV-2 infection (strict-term) within 14 days of a positive RT-qPCR at baseline or during the EAP	C	X	X
Proportion of subjects with viral load >4 (log10 copies/mL) in NP swab samples during the EAP	B	X	X
Change in viral load (log10 copies/mL) from baseline to Day 8 visit in NP swab samples	C	X	X
Change in viral load (log10 copies/mL) from baseline to Day 15 visit in NP swab samples	C	X	X
Time-weighted average change from baseline in viral load (log10 copies/mL) in NP swab samples until the Day 22 visit	C	X	X
Area under the curve (AUC) in viral load (log10 copies/mL) in NP swab samples from baseline to the first confirmed negative test	C	X	X
Maximum SARS-CoV-2 RT-qPCR viral load (log10 copies/mL) in NP swab samples during the EAP	C	X	X
Number of medically attended visits in emergency rooms or urgent care centers related to RT-qPCR confirmed SARS-CoV-2 infection that has an onset at baseline or during the EAP	C	X	X
Proportion of subjects requiring medically attended visits in emergency rooms or urgent care centers related to a RT-qPCR confirmed SARS-CoV-2 infection that has an onset at baseline or during the EAP	B	X	X
Proportion of subjects hospitalized related to a RT-qPCR confirmed SARS-CoV-2 infection that has an onset at baseline or during the EAP	B	X	X
Number of days of hospital and ICU stay in subjects hospitalized for a RT-qPCR confirmed SARS-CoV-2 infection that has an onset at baseline or during the EAP	C	X	X
Number of days missed for daily responsibilities (where applicable), including work (employed adults) or school	C	X	X

(students), or family obligations/responsibilities (childcare or eldercare) due to a RT-qPCR confirmed SARS-CoV-2 infection that has an onset at baseline or during the EAP			
Proportion of subjects with at least one COVID-19 related hospitalization or emergency room visit associated with a positive RT-qPCR at baseline or during the EAP, or all-cause death	B	X	X
Proportion of subjects who subsequently develop signs and symptoms (broad-term) within 14 days of a positive RT-qPCR at baseline or during the EAP	B		X
Number of weeks of symptomatic SARS-CoV-2 infection (broad-term) within 14 days of a positive RT-qPCR at baseline or during the EAP	C		X
Number of weeks of high viral load >4 (log10 copies/mL) in NP swab samples during the EAP	C		X

Time-weighted average (TWA) of change from baseline in viral load until the Day 22 visit: All observed viral load data from baseline to Day 22 visit will be calculated for each subject using the trapezoidal rule as the AUC for change from baseline at each time point divided by the time interval of this observational period as follows:

$$TWA = AUC/(t_k - t_1) = [\sum_{i=2}^{k=4} (t_i - t_{i-1}) * (D_i + D_{i-1})/2]/(t_k - t_1)$$

Where D_i is the change from baseline (t_1) in viral load (log10 copies/mL) obtained at time t_i and $D_1 = 0$. If the D_i is not available or missing due to failed test or other reasons, only the time points with non-missing values will be included for TWA calculation. If there are duplicate samples at a time point, the highest viral result (log10 copies/ml) will be used for analysis.

For TWA of percent change from baseline, variable P_i will be applied to the formula above instead of D_i , where $P_i = D_i/\text{baseline}$.

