#### **4.2.4. Cohort B and Cohort B1 Exploratory Endpoints**

- Proportion of subjects who subsequently have symptomatic (strict-term) SARS-CoV-2 infection confirmed by RT-qPCR within the EAP according to their baseline serology test status (ie, seropositive or other, based on central lab test)
- Proportion of subjects who subsequently have symptomatic (broad-term) SARS-CoV-2 infection confirmed by RT-qPCR within the EAP according to their baseline serology test status (ie, seropositive or other, based on central lab test)
- Proportion of subjects who subsequently have symptomatic (CDC definition) SARS-CoV-2 infection confirmed by RT-qPCR within the EAP according to baseline serology test status (ie, seropositive or other, based on central lab test)
- Number of weeks of symptomatic SARS-CoV-2 infection (strict-term) within 14 days of a positive RT-qPCR at baseline or during the EAP, according to baseline serology test status (ie, seropositive or other, based on central lab test)
- Number of weeks of symptomatic SARS-CoV-2 infection (broad-term) within 14 days of a positive RT-qPCR at baseline or during the EAP, according to baseline serology test status (ie, seropositive or other, based on central lab test)
- Number of weeks of symptomatic SARS-CoV-2 infection (CDC definition) within 14 days of a positive RT-qPCR at baseline or during the EAP, according to baseline serology test status (ie, seropositive or other, based on central lab test)
- Time-weighted average change and percent change from baseline viral load ( $\log_{10}$  copies/mL) by SARS-CoV-2 RT-qPCR in NP swab samples until the day 22 visit

according to baseline serology test status (ie, seropositive or other, based on central lab test)

- Area under the curve (AUC) in viral load ( $\log_{10}$  copies/mL) in NP swab samples from baseline to the first confirmed negative test according to baseline serology test status (ie, seropositive or other, based on central lab test)
- Maximum SARS-CoV-2 RT-qPCR ( $\log_{10}$  viral copies/mL) in NP swab samples during the EAP according to baseline serology test status (ie, seropositive or other, based on central lab test)
- Number of medically attended visits in emergency rooms or urgent care centers related to RT-qPCR confirmed SARS-CoV-2 infection at baseline or during the EAP, according to baseline serology test status (ie, seropositive or other, based on central lab test)

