The following general rules will be used for efficacy variables and all SARS-CoV-2 RT-qPCR test results are based on the central lab testing:

- For cohort determination, qualitative PCR results from swabs taken prior to or within 2 hours of study drug administration will be used if there are no available test results prior to study drug administration.
- Quantitative values of viral load will be determined based on NP swabs only. For baseline viral load, only RT-qPCR results from swabs taken prior to dosing will be used.
- A positive infection will be defined based on any available RT-qPCR result (either NP, nasal or saliva) which is reported as “detected”. A negative infection will be defined based on all available RT-qPCR results (either NP, nasal or saliva) which are reported as “not detected”.
- Symptomatic SARS-CoV-2 infection (broad-term) is defined as a positive central lab SARS-CoV-2 RT-qPCR result (either NP, nasal or saliva) associated with signs and symptoms with the onset date occurring within 14 days of a positive RT-qPCR during the EAP.
- For subjects in Cohort B, symptomatic SARS-CoV-2 infection (broad-term) is defined as having at least one signs and symptoms with the onset date occurring within 14 days of a positive RT-qPCR (either NP, nasal or saliva) at baseline or during the EAP.

- Viral loads less than the lower limit of quantification of the PCR assay but with positive qualitative results will be set to half of the lower limit of quantification of the PCR assay; values with nondetectable RNA will be set to 0 log₁₀ copies/mL. Viral load values above the upper limit of quantification will be re-tested using the reflex test and the corresponding quantitative value will be used in the analysis.

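### The exploratory cohort B/B1 percent change in viral load is a log10 change divided by a log10 baseline, so it does not measure a percent change in virus

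*SAP*

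**What the plan says.** SAP 4.5.7 defines the time-weighted average (TWA) change to day 22 by the trapezoidal rule, where "D_i is the change from baseline (t_1) in viral load (log10 copies/mL) obtained at time t_i". It then adds the percent version: "For TWA of percent change from baseline", "variable P_i will be applied to the formula above instead of D_i", with P_i equal to D_i divided by baseline. There is no rule for a baseline of zero.

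The endpoint itself, "Time-weighted average change and percent change from baseline viral load", is listed in Protocol 4.2.4 and SAP 4.5.8. Both label it in log10 copies/mL and place it among the exploratory variables for cohorts B and B1, by baseline serology. The secondary lists (Protocol 4.2.3, SAP 4.5.7) contain only the absolute TWA change.

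SAP 5.7.4 names the percent version among the cohort B endpoints for ANCOVA, with treatment, region, age group, baseline and a treatment-by-baseline interaction. A least-squares mean difference, standard error and 95% CI are to be reported.

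Four general rules in SAP 4.5 bear on the denominator:
- "Quantitative values of viral load will be determined based on NP swabs only", and baseline load comes only from swabs taken before dosing.
- A subject counts as positive on an NP, nasal or saliva sample.
- For results below the quantification limit, "values with nondetectable RNA will be set to 0" log10 copies/mL.
- Values below that limit "with positive qualitative results will be set to half of the lower limit of quantification of the PCR assay".

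**The concern.** A reader who sees a percent change in viral load will take it as the share of virus removed. A difference of two log10 values is already a relative measure, because it is the logarithm of the fold-change. Dividing it by the log10 of the starting concentration removes that meaning. The quotient depends on where the subject started and on the unit in which concentration is expressed.

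What is at stake is an inferential result, with a confidence interval, that can be misread as percent reduction in virus. Because results are shown by serostatus, any difference in baseline load between the serology groups would also change the scale on which the groups are compared. The documents do not give those baseline loads.

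**Working it through.** **Inputs.** D_i, P_i and the TWA formula come from SAP 4.5.7, and the coding rules from SAP 4.5. The trajectories are assumptions, because the documents give no cohort B viral-load data. The plan states no figure on this point to reproduce. P is shown multiplied by 100.

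**Scale of the denominator.** The formula does not state it separately, but the endpoint is labelled in log10 copies/mL, so I read it that way. Reading it as raw copies would not help: a 2 log10 fall from 4 log10 would give -2/10,000 = -0.02%.

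**Step 1: one visit, same fall.** Take D = -2, a 100-fold fall. The true percent change is 10^(-2) - 1 = -99% at every baseline.

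| Baseline, log10 copies/mL | P = D/baseline |
|---|---|
| 8 | -2/8 = -25% |
| 7 | -2/7 = -29% |
| 4 | -2/4 = -50% |

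**Step 2: the TWA.** Baseline is constant within a subject, so TWA of P = (TWA of D)/baseline. For a fall of 1 log10 per week over days 1, 8, 15 and 22, D = 0, -1, -2, -3. Then TWA of D = 7 × (-0.5 - 1.5 - 2.5)/21 = -1.50. Moving to copies/L adds 3 to every log10 value, and moving to copies/µL subtracts 3. D does not change; the denominator does.

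| Baseline, log10 copies/mL | TWA of D, any unit | TWA of P, copies/mL | copies/L | copies/µL |
|---|---|---|---|---|
| 7 | -1.50 | -21.4% | -1.5/10 = -15.0% | -1.5/4 = -37.5% |
| 5 | -1.50 | -30.0% | -1.5/8 = -18.75% | -1.5/2 = -75.0% |

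**Step 3: ordering of subjects.** Non-detection is coded 0, so a subject who clears scores (0 - B)/B = -100% at that visit, whatever the baseline B.
- Path 7, 4, 0, 0: TWA of D = -4.50, TWA of P = -64.3%.
- Path 4, 2, 0, 0: TWA of D = -2.67, TWA of P = -66.7%.

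The subject with the larger log10 fall has the smaller percent score.

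**Step 4: the ANCOVA.** A constant treatment effect of -1 log10 becomes -1/8 = -12.5 points at baseline 8 and -1/4 = -25 points at baseline 4. Division by baseline therefore creates a treatment-by-baseline interaction where none exists on the log10 scale. It has the form 1/baseline, which a linear interaction term can only approximate.

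**Step 5: a zero denominator.**
- Positive NP swab, quantifiable: baseline is the measured value.
- Positive NP swab below the quantification limit: half that limit. The limit is not given, nor whether the halving is on the copies or the log10 scale. For assumed limits of 50 to 5000 copies/mL the result is 1.40 to 3.40 log10 if copies are halved, or 0.85 to 1.85 if the log10 value is halved. Neither is zero.
- No pre-dose NP swab: baseline is missing, not zero.
- Pre-dose NP swab non-detected with a positive nasal or saliva sample: baseline is 0 and P is undefined. For the path 0, 3, 2, 0 the TWA of D is +1.67, but P cannot be computed.

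Only the last case fails, and the SAP has no rule for it.

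**The case against.** The strongest reply is that the unit is fixed throughout at log10 copies/mL, so nobody will compute the per-litre figure. With non-detection coded 0, P can be read as the fraction of log10 baseline cleared. The ANCOVA adjusts for baseline and its interaction with treatment, and the endpoint is exploratory. The fixed unit does make the value computable, and the exploratory status limits the impact. But the fraction-of-log10 reading is still anchored to an arbitrary unit, since 0 log10 means one copy per mL, and it is not what the label says. Adjusting for baseline does not turn a ratio of logs into a percent change.

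Three stronger readings are tempting, and the documents do not support them:
- **That the endpoint is undefined for some subjects.** Cohort B is RT-qPCR positive at baseline by definition, and low positives receive half the quantification limit. A zero needs discordant specimens. Protocol 9.2.2.1 collects only NP swabs for the central test, and the amendment history records that nasal and saliva collection ended at Amendment 1. No discordant subject is shown.
- **That low-baseline subjects dominate the estimate, or that it contradicts the log10 analysis.** The weight is 1/baseline, so a subject at 4 log10 counts twice as much per log10 as one at 8. That is a tilt. No group estimate shows domination, and within any subject with a positive baseline P and D have the same sign.
- **That a secondary endpoint is affected.** The formula sits in the secondary section of the SAP, but the percent version is listed only as exploratory.

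**Conclusion.** The defect is one of definition and applies to every subject for whom the variable can be computed. The reported percent change is a ratio of logarithms: a 99% fall in virus is scored as -25% or -50% according to whether baseline is 8 or 4 log10 copies/mL. This rests only on reading the denominator as log10 copies/mL, as the endpoint label states. The unit and weighting results follow by arithmetic; the trajectories are illustrative. The undefined case is a gap in the rules whose frequency is unknown and may be nil.

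The consequence is small. The endpoint is exploratory and outside the cohort B hierarchy in SAP 5.7.2, and no sample size or error rate depends on it. The correction is worth making because it is nearly free and prevents a misleading number from being reported.

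**What to change.** Delete the percent version in four places: the formula sentence at the end of SAP 4.5.7, the exploratory row in SAP 4.5.8, the mention in SAP 5.7.4, and the endpoint in Protocol 4.2.4. For the exploratory analysis by serostatus, report the TWA change in log10 copies/mL with baseline as covariate, which SAP 4.5.7 and 5.7.4 already specify.

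If a relative measure is wanted, back-transform. With D the log10 change, the fold-change is 10^D and the percent change is 10^D - 1. For the trajectory in Step 2, 10^(-1.5) = 0.032, a reduction of about 97% whether baseline is 7 or 5 and in any unit. The treatment difference back-transforms in the same way to a ratio between arms.

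The cost is one exploratory variant. Because the protocol lists it and SAP 1.2.4 declares no modifications from Amendment 6, the removal must be recorded there as a departure, or the protocol amended. If the sponsor prefers to keep the variable, the minimum is to label it as a ratio of log10 values and state how a non-detected baseline NP swab is handled.

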4.5.8. Cohort B and Cohort B1 Exploratory Variables

The following exploratory variables are for both Cohort B and Cohort B1.

Exploratory Variables	Type
Proportion of subjects who subsequently have symptomatic (strict-term) SARS-CoV-2 infection confirmed by RT-qPCR within the EAP according to their baseline serology test status (i.e., seropositive or other, based on central lab test)	B

Proportion of subjects who subsequently have symptomatic (broad-term) SARS-CoV-2 infection confirmed by RT-qPCR within the EAP according to their baseline serology test status (i.e., seropositive or other, based on central lab test)	B
Proportion of subjects who subsequently have symptomatic (CDC definition) SARS-CoV-2 infection confirmed by RT-qPCR within the EAP according to baseline serology test status (i.e., seropositive or other, based on central lab test)	B
Number of weeks of symptomatic SARS-CoV-2 infection (strict-term) within 14 days of a positive RT-qPCR at baseline or during the EAP, according to baseline serology test status (i.e., seropositive or other, based on central lab test)	C
Number of weeks of symptomatic SARS-CoV-2 infection (broad-term) within 14 days of a positive RT-qPCR at baseline or during the EAP, according to baseline serology test status (i.e., seropositive or other, based on central lab test)	C
Number of weeks of symptomatic SARS-CoV-2 infection (CDC definition) within 14 days of a positive RT-qPCR at baseline or during the EAP, according to baseline serology test status (i.e., seropositive or other, based on central lab test)	C
Time-weighted average change and percent change from baseline viral load (log ₁₀ copies/mL) in NP swab samples until the Day 22 visit according to baseline serology test status (i.e., seropositive or other, based on central lab test)	C
Area under the curve (AUC) in viral load (log ₁₀ copies/mL) in NP swab samples from baseline to the first confirmed negative test according to baseline serology test status (i.e., seropositive or other, based on central lab test)	C
Maximum SARS-CoV-2 RT-qPCR (log ₁₀ viral copies/mL) in NP swab samples during the EAP according to baseline serology test status (i.e., seropositive or other, based on central lab test)	C
Number of medically attended visits in emergency rooms or urgent care centers related to RT-qPCR confirmed SARS-CoV-2 infection at baseline or during the EAP, according to baseline serology test status (i.e., seropositive or other, based on central lab test)	C
Proportion of subjects requiring medically attended visits in emergency rooms or urgent care centers related to a RT-qPCR confirmed SARS-CoV-2 infection at baseline or during the EAP, according to baseline serology test status (i.e., seropositive or other, based on central lab test)	B
Proportion of subjects hospitalized related to a RT-qPCR confirmed SARS-CoV-2 infection at baseline or during the EAP, according to baseline serology test status (i.e., seropositive or other, based on central lab test)	B

Number of days of hospital and ICU stay in subjects hospitalized for a RT-qPCR confirmed SARS-CoV-2 infection at baseline or during the EAP, according to baseline serology test status (i.e., seropositive or other, based on central lab test)	C
Number of days missed for daily responsibilities (where applicable), including work (employed adults) or school (matriculating students), or family obligations/responsibilities (childcare or eldercare) due to a RT-qPCR confirmed SARS-CoV-2 infection at baseline or during the EAP, according to baseline serology test status (i.e., seropositive or other, based on central lab test)	C
Maximum RT-qPCR viral load (log10 copies/mL) in NP swab samples during the EAP in subjects who have asymptomatic infection during the EAP	C
Maximum RT-qPCR viral load (log10 copies/mL) in NP swab samples during the EAP in subjects who have symptomatic infection during the EAP	C
Maximum RT-qPCR viral load (log10 copies/mL) in NP swab samples during the EAP in subjects who have a medically attended visit related to a RT-qPCR confirmed SARS-CoV-2 infection at baseline or during the EAP	C

4.6. Safety Variables

4.6.1. Adverse Events and Serious Adverse Events

Adverse events and serious adverse events will be collected from the time of informed consent signature and then at each visit until the end of the study. All adverse events are to be coded to a “Preferred Term (PT)” and associated primary “System Organ Class (SOC)” according to the Medical Dictionary for Regulatory Activities (MedDRA version 23.1). The severity of AEs (including test findings classified as AEs) and injection-site -related reactions will be graded by the investigator using the current version of the NCI-CTCAE v5.0 0. The NCI-CTCAE severity grading systems for anaphylaxis, allergic reaction, and injection site reaction are specifically in section 10.2.4 of the protocol.

An adverse event is any untoward medical occurrence in a subject or clinical investigation subject administered a pharmaceutical product and which does not necessarily have to have a causal relationship with this treatment.

A serious adverse event is an adverse event (AE) that is classified as serious according to the criteria specified in the protocol.

For safety variables, the following observation periods are defined:

- The pre-treatment period is defined as the time from signing the ICF to before the first dose of study drug.
- The treatment-emergent EAP (TEEAP) is defined as the day from first dose of study drug to 28 days after the last dose of study drug (Note: There is only one planned dose.)
- The treatment-emergent follow-up period (TEFUP) is defined from the day after the end of the TEEAP to the end of the Follow-up Period (i.e., last study visit).

Treatment-emergent adverse events (TEAEs) are defined as those that are not present at baseline or represent the exacerbation of a pre-existing condition.

Treatment-emergent adverse events (TEAEs) will be summarized for each of the following periods: treatment-emergent EAP, treatment-emergent follow-up period, and the study period (i.e. combination of the treatment-emergent EAP and follow-up periods). Adverse events that occur prior to treatment will be listed.

Laboratory results, physical examination, and vital signs are to be recorded as AEs if they are medically relevant: symptomatic, requiring corrective therapy, leading to study discontinuation and/or fulfilling a seriousness criterion.

